3.5 Source data

The following data will be collected onto the Case Report Forms (CRFs) at the corresponding times.

3.5.1 Data for eligibility

Data for potential eligibility will be collected as per the inclusion and exclusion criteria

3.5.2 Data for randomisation

For randomisation the following extra data is collected:

Mother's expected date of delivery Birth date

3.5.3 Identifying information

The following identifiable data will be collected. Identifying data will be kept at each local site in locked filing cabinets.

Child's name Family address and phone numbers Child's paediatrician or family doctor An alternate contact to find the family

3.5.4 Medical and social history

The following medical and social history data will be collected:

Language spoken at home Family structure with details of parents including who is primary income earner, who is primary carer and details of employment status and education Maternal age at birth of child Presence in family of anyone with a mental or learning disorder Gender Method of calculating expected date of delivery Birth weight, in kg Apgar score at 1 and 5 minutes, mode of delivery, if the child was part of a multiple pregnancy, presence of labour, antenatal steroids, history of prolonged rupture of membranes, pre-eclampsia or chorioamnionitis History and details of previous apnoea or respiratory support Details of any previous neurological injury or intraventricular haemorrhage Previous ROP or hearing defects Previous sepsis Days the child spent in hospital after birth and date child last discharged from hospital

3.5.5 Pre anaesthesia details. Both regional and general groups

The following data will be collected prior to anaesthesia:

Date of surgery Current respiratory support Current medication Weight Timing and details of last feed Baseline HR, NIBP, SpO₂, temperature in a calm comforted child Details of premedication and fluids

3.5.6 Anaesthesia details

The following data during anaesthesia will be collected

3.5.6.1 Anaesthesia details. Regional group only

Seniority of anaesthetist Times for anaesthesia blocks and surgery Blocks used and details of block technique including position of child, dose and concentration of bupivacaine or levobupivacaine, number of needle passes, presence of blood in needle and flow of CSF through needle Distress of child and SpO₂ and HR during the block Volume and type of fluid given in theatre Blood glucose and haemoglobin Details of any rescue therapy for low glucose, hypotension or hypoxia Efficacy of block and activity of child during the procedure Details of any respiratory support or apnoea during procedure HR, NIBP, SpO₂ and activity of child every 5 minutes during surgery

3.5.6.2 Anaesthesia details. General group only

Seniority of anaesthetist Times for anaesthesia induction and times for blocks and surgery Blocks used and details of block technique including dose and concentration of bupivacaine or levobupivacaine, number of needle passes, presence of blood in needle and flow of CSF through needle Details of anaesthesia induction Details of airway management and use of any NDNMB Volume and type of fluid given in theatre Blood glucose and haemoglobin Details of any rescue therapy for low glucose, hypotension or hypoxia Efficacy of blocks Details of awakening, airway removal and reversal of any NDNMB Details of any respiratory complications or apnoea during awakening or after airway removed. HR, NIBP, Inspiratory oxygen, SpO₂ and End tidal CO₂ and sevoflurane concentrations every 5 minutes during surgery

The total dose of sevoflurane will be calculated as concentration*hours dose equivalent

3.5.6.3 Details of protocol violations

Details of any protocol violation including need for opioids or nitrous oxide Details of management for failed block

3.5.7 Surgical details

The following surgical data will be collected:

Presence of unilateral or bilateral hernia on pre-op exam Unilateral or bilateral exploration and presence of unilateral or bilateral hernia on exploration Seniority of surgeon

3.5.8 Post anaesthesia care unit data

In PACU (or during the first 30 minutes on the ward if PACU is bypassed) the following adapt will be collected:

Details of monitoring for apnoea Drugs given Number of significant apnoeas Details of any intervention for apnoea or respiratory support needed HR, NIBP, SpO₂ every 5 minutes during PACU stay and lowest SpO₂ FALCC scores and details of any analgesia Presence of stridor Time to first feed Sunken fontanel, any persistent CSF leak

3.5.9 Post PACU details

For the 12 hours after PACU or up until routine discharge the following data will be collected.

Details of monitoring for apnoea Drugs given Details of any intervention for apnoea or respiratory support needed Number of significant apnoeas Presence of stridor Time child discharged home

3.5.10 Follow-up day 1-5

In the period from 1-5 days post anaesthesia the following data will be collected where relevant.

Day discharged home Details of any medical interventions initiated on day 1-5 Was the child readmitted to hospital? Details of any evidence for infection associated with nerve blockade or presence of stridor

If child stays longer than 5 days:

Length of stay in hospital

Details of any medical intervention in the period between surgery and discharge from hospital

3.6 Details of apnoea data collection

At all sites heart rate, respiration and oxygen saturation will be continuously recorded in PACU. This data may be downloaded electronically. Details of any intervention for apnoea in PACU will be recorded. An activity sheet will be completed to identify feeding and other activity that may contribute to artefact when data is electronically collected.

After PACU all sites will monitor for apnoea using their established practices. For all patients any post-PACU intervention or change in management due to apnoea will be recorded. After PACU some children will have continuous monitoring with heart rate oxygen saturation oximetry and respiratory rate for up to 24 hours. This data may be recorded and downloaded electronically. As for PACU electronic data will be accompanied by an activity sheet.

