3. STUDY DESIGN

3.1 Experimental Design: Prospective, observer blind, multi-site, randomised, controlled, equivalence trial

3.2 Randomisation: Randomisation to either of the two treatment groups (GA or RA) will be by block and stratified by site and gestational age at birth. Gestational age at birth strata will be:

- 26 weeks to 29 weeks and 6 days
- 30 weeks to 36 weeks and 6 days
- 37 weeks and more

Access to randomisation numbers will be via a 24 hour web-based randomisation service set up and maintained by A/[name] at The Data Management & Analysis Centre, Department of Public Health, University of Adelaide, South Australia: http://www.dmac.adelaide.edu.au/gasRandomisation

Entry to the website is password protected.

3.3 Blinding: The anaesthetist will be aware of the group allocation. The psychologist and paediatrician performing the 2 and 5 year neurodevelopmental assessments will be blinded to study group. Parents will not be told which group their child was in but they will be allowed to discover the group and will be told if asked. Parents will be clearly instructed that if they do discover the group then they should not inform the assessing psychologist. A record will be made of whether or not the parents or the psychologist became aware of the allocation. The apnoea assessment and recovery assessment will not be blinded.

3.4 Study duration: The duration of subject participation is five years.

- Children will be enrolled before surgery.
- Data will be collected before and during anaesthesia and in the early postoperative period.
- Formal neurodevelopmental assessment will occur at 2 and 5 years corrected age (see appendix 1 for definition of corrected age).

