6.2.2 Apnoea

Apnoea will be defined in terms of changes in recorded vital signs and need for intervention. The timing of the apnoea will also be early or late.

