6.2.2.1 Significant apnoea by vital signs

A significant apnoea will be defined as a pause in breathing of greater than 15 seconds or a pause greater than 10 seconds if associated with oxygen saturation <80% or bradycardia (20% fall in heart rate).

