8.2 Analyses of Secondary outcomes

8.2.1 Other measures of neurodevelopmental outcome

A per-protocol analysis of the mean difference of the Cognitive component of the Bayley III scale between arms adjusted for gestational age will be presented with a 2-sided 95% confidence interval. Equivalence will be accepted if the confidence interval of the difference in means lies within -5 and +5 points.

For other continuous data, groups will be compared as for the primary outcome with the gestation-adjusted mean difference in scores presented with a 2-sided 95% confidence interval. For frequency data difference in frequency between groups will be presented with a 2-sided 95% confidence interval.

8.2.2 Apnoea:

There will be four Apnoea outcomes.

- Early significant apnoea on vital signs
- Late significant apnoea on vital signs
- Intervention for early apnoea
- Intervention for late apnoea

For each apnoea outcome an adjusted regression analysis will be performed to assess associations between risk factors and apnoea.

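### Early apnoea on vital signs needs pauses timed to 10 or 15 seconds, but download of the PACU recording is optional and the form's apnoea count has no stated source

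*Protocol*

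**What the plan says.** Section 6.2.2 sets the basis of the outcome: "Apnoea will be defined in terms of changes in recorded vital signs and need for intervention". Section 6.2.2.1 gives the thresholds: "a pause in breathing of greater than 15 seconds or a pause greater than 10 seconds if associated with oxygen saturation" below 80%, or if the heart rate falls by 20%. Section 8.2.2 lists "Early significant apnoea on vital signs" as one of four apnoea outcomes, separate from intervention for early apnoea.

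On data capture, section 3.6 is firm about recording and permissive about retrieval: "At all sites heart rate, respiration and oxygen saturation will be continuously recorded in PACU. This data may be downloaded electronically". It also provides an activity sheet to help recognise artefact in electronically collected data.

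The PACU form in 3.5.8 charts heart rate, blood pressure and saturation every 5 minutes. It also takes the lowest saturation, details of how apnoea was monitored, and the item "Number of significant apnoeas". It charts no respiration and names no source for that count.

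Section 3.3 adds: "The apnoea assessment and recovery assessment will not be blinded".

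**The concern.** The definition requires someone to time a pause to within seconds and line it up with two other signals. The continuous recording can show this, but the protocol does not require that it be downloaded or kept, or that the count be taken from it. One site may score a trace while another enters what a nurse noticed, and both entries go into the same form item.

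Two things are at stake.

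- **Direction.** Sections 1.4.3 and 11 record a prior expectation that regional anaesthesia brings less apnoea. Staff who count at the bedside know the allocation, so that expectation can enter the count.
- **Comparability.** Section 1.4.3 criticises the earlier trials for measuring apnoea in different ways. Optional download permits the same between sites here. In the risk-factor regressions of 8.2.2, a difference in detection between sites can then look like an association with whatever patient features differ between those sites.

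Apnoea is in the trial's title and is secondary aim 2.2.2, and the data monitoring committee considers its rate in each group (7.2). Which data are kept is settled at collection. A later analysis plan cannot recover a recording that was not retained.

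**Working it through.** The protocol gives no figure for this point, so there is none to reproduce. The check is first textual.

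1. **What the definition needs (6.2.2, 6.2.2.1):** recorded signals, pause length to the second, and concurrent saturation or heart rate.
2. **What is certain to exist (3.6):** a continuous recording of all three signals in PACU, at every site.
3. **What is certain to reach the database (3.5.8):** 5-minute heart rate, blood pressure and saturation, the lowest saturation, and a count without a source. The lowest saturation shows a nadir, not a pause.
4. **Whether another section closes the gap:** section 7.1 requires respiratory rate to be monitored in PACU but says nothing on keeping it. Section 9 describes the flow of case report forms, not of monitor files. Neither closes it.
5. **Whether the recording spans the outcome:** early apnoea (6.2.2.3) also includes the operating room after surgery, and the first 30 minutes in NICU when PACU is bypassed. The recording requirement in 3.6 names PACU only.

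The illustration below shows how the size depends on unknowns. **None of its inputs are in the protocol.** Let p be the true early apnoea rate, q the share of children without a trace (equal in both arms), and s the bedside sensitivity. The trace is taken as fully sensitive, and false positives are ignored.

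Observed rate = p × [(1 − q) + q × s]

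With p = 5% in both arms, s = 0.80 under general anaesthesia (GA) and s = 0.60 under regional anaesthesia (RA):

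| q | GA observed | RA observed | Difference (points) | Ratio |
|---|---|---|---|---|
| 0 | 5.00% | 5.00% | 0 | 1.00 |
| 25% | 0.05 × (0.75 + 0.20) = 4.75% | 0.05 × (0.75 + 0.15) = 4.50% | 0.25 | 1.06 |
| 50% | 0.05 × (0.50 + 0.40) = 4.50% | 0.05 × (0.50 + 0.30) = 4.00% | 0.50 | 1.13 |
| 100% | 0.05 × 0.80 = 4.00% | 0.05 × 0.60 = 3.00% | 1.00 | 1.33 |

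The ratio does not depend on p. At q = 100% the difference is 0.6 points for p = 3% and 2.0 points for p = 10%.

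If s = 0.60 in both arms, the spurious difference is 0, but both rates are understated by 0.40 × q: 10%, 20% and 40% for q = 25%, 50% and 100%.

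Between sites, one that scores every trace would report 5% and one that scores none would report 0.05 × 0.60 = 3%. That is a ratio of 1.67 with no true difference.

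**The case against.** The best defence is that recording is mandatory, so a file that is not exported is not a trace that never existed. Staff can read a pause from the monitor or its stored record. The form also takes details of apnoea monitoring, which may let an analyst separate counts by method. This stands in part: bedside impression is something the wording permits, not something it prescribes. But nothing requires staff to consult the monitor's record.

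Second, the harm is bounded. The apnoea aim is descriptive, no apnoea hypothesis is listed in 2.3, and the lack of blinding is openly declared. Randomisation is stratified by site, so site differences in download should fall roughly evenly on the two arms. All of this stands. It leaves unblinded counting within a site, understated rates, and the risk-factor regressions.

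Stronger readings that a reader might infer are not supported:

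- **That many counts will be bedside impressions.** The share without download is not stated.
- **That every child has a trace for the whole early window.** The operating room and PACU-bypass periods have no promised recording.
- **That trace and bedside counts are pooled by rule.** Section 8.2.2 names the outcome and a regression. It states no rule on sources either way.
- **That 5-minute charting measures the loss.** A charting point falls inside a 10-second pause with probability 10/300 = 3.3%, and inside a 15-second pause with 15/300 = 5%. The apnoea count is a separate form item, so these figures do not describe how it is made.

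**Conclusion.** The point holds in limited form. The protocol defines an outcome by timed, recorded signals, makes retrieval of those signals optional, accepts a count of unstated origin, and leaves the assessment unblinded. An unknown share of early vital-sign counts may therefore rest on bedside observation that varies by site.

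The size cannot be fixed from the document. The illustrated range rests wholly on the assumed rates and sensitivities. It is zero between arms if detection is equal, and zero altogether if every trace is used. Download alone would not settle the matter, because no reading of the trace without the allocation is specified. This concerns a secondary outcome. It is worth correcting because the protocol already requires the recording and the change is cheap.

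**What to change.** - **Section 3.6:** state that the PACU recording will be retained, and downloaded wherever the monitor allows export. Score it with a program that applies the 6.2.2.1 thresholds without access to the allocation, using the activity sheet to deal with artefact.
- **Section 3.5.8:** record the source of each apnoea count, trace or bedside observation.
- **Section 8.2.2:** make the trace-derived count the main early vital-sign outcome for PACU time. Report bedside counts separately, including those from the operating room and from NICU when PACU is bypassed. Do not set these to missing: that would selectively drop infants who bypass PACU and events in the operating room, both of which 6.2.2.3 counts.
- **Reporting:** give the share of children with a usable trace by arm and by site.

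The cost is file-transfer work and one scoring program. Some sites may be unable to export, since the protocol does not state their capability, and trace coverage of this secondary outcome will be incomplete.

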3.7 Two year assessment data

The following data will be collected at 2 years corrected age.

3.7.1 Data for family/environmental factors at two years

Support for special needs such as audiologist, optometrist, physiotherapy, speech/language therapy, occupational therapy, orthoptist, psychologist.

Child Care arrangements, if child attends playgroup and age started at group. Social history as per 3.5.4

3.7.2 Medical history at two years

Details of all hospital attendances and admissions to hospital after discharge following hernia repair. Exposure to any anaesthetic agents or benzodiazepines since discharge from hospital after hernia repair.

Details of any recurrence of hernia on either side since repair

3.7.3 Neurodevelopmental assessment at two years:

- Bayley Scales of Infant Development III (BSID-III): Cognitive, language and motor scales
- Paediatric assessment including neurological examination to determine presence of cerebral palsy
- Visual and hearing acuity tests
- Delayed Alternation and Spatial Reversal Tasks (Espy) [An experimental task]

It will be noted whether or not the parent or psychologists are aware of allocation.

3.8 Five years assessment data

The following data will be collected at 5 years corrected age.

3.8.1 Data for family/environmental factors at five years

Data as per 3.7.1

3.8.2 Medical history at five years

Details of all hospital attendances and admissions to hospital since 2 year assessment

Details of any recurrence of hernia on either side since repair Details of any intervention initiated as a result of the findings at the 2 year neurodevelopmental assessment

3.8.3 Neurodevelopmental assessment at five years

- A paediatric assessment as per 2 years
- General intellectual ability, Verbal, Visuo-spatial and Processing Speed Skills from the Wechsler Preschool and Primary Scale of Intelligence - Third Edition (WPPSI-III)
- Auditory and visual attention will be assessed using the NEPSY tasks
- The behavioural features of executive dysfunction will be assessed via the behavioural Rating of Executive Function (BRIEF)

It will be noted whether or not the parent or psychologists are aware of allocation.

4. SELECTION OF SUBJECTS

4.1 Number of subjects: 660

4.2 Inclusion criteria: Any child scheduled for unilateral or bilateral inguinal hernia repair (with or without circumcision).

4.3 Exclusion criteria:

- Any child older than 60 weeks postmenstrual age
- Any child born at less than 26 weeks gestation
- Any contraindication to general *or* spinal/caudal anaesthesia (for example: neuromuscular disorder or coagulopathy)
- Pre-operative ventilation immediately prior to surgery
- Congenital heart disease that has required surgery or will require surgery or which requires ongoing pharmacotherapy
- Known chromosomal abnormality or any other known acquired or congenital abnormalities (apart from prematurity) which are likely to affect development
- Children where follow-up would be difficult for geographic or social reasons
- Families where the primary language spoken at home is *not* the language in which the WPPSI-III will be given [i.e. English for Australian sites, French for Paris site and English or Spanish for US sites]
- Known neurological injury such as cystic periventricular leukomalacia (PVL), or grade 3 or 4 intra ventricular haemorrhage (IVH) (+/- post haemorrhage ventricular dilatation)
- Previous exposure to volatile anaesthesia or benzodiazepines as a neonate or in the third trimester in utero

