AE: Non serious adverse events BCH: Boston Children's Hospital, Boston BRIEF: Behavioural rating of executive function BSID-III: Bayley scales of infant development, version III CPAP: Continuous positive airway pressure CRF: Case report form CSF: Cerebrospinal fluid DMC: Data monitoring committee ECG: Electrocardiograph ESPY: Experimental Delayed Alternation and Spatial Reversal Tasks FLACC: Behavioural scale for scoring postoperative pain in young children measured in 5 areas: face, legs, activity, cry, consolability GA: General anaesthesia GABA: Gamma amino butyric acid HR: Heart rate IV: Intra venous IVH: Intra ventricular haemorrhage NDNMB: Non-depolarizing neuromuscular blocking agent NEPSY: Developmental neuropsychological assessment NIBP: Non invasive blood pressure NICU: Neonatal Intensive Care Unit or Neonatal unit NMDA: n-methyl-d-aspartic acid PACU: Post anaesthesia care unit - also known as the recovery ward PI: Principal investigator PMA: Postmenstrual age (see appendix one) PVL: Peri ventricular leukomalacia RA: Regional anaesthesia RCH: Royal Children's Hospital, Melbourne ROP: Retinopathy of prematurity SAE: Serious adverse events SAR: Serious adverse reaction SUSAR: Suspected unexpected serious adverse events TSC: Trial steering committee UTI: Urinary tract infection WPPSI-III: Wechsler preschool and primary scale of intelligence- Third Edition

SYNOPSIS

Title: A multi-site RCT comparing regional and general anaesthesia for effects on neurodevelopmental outcome and apnoea in infants

Chief investigators: [name] (PI), [name](PI), [name], [name], [name], [name], [name], [name], [name]

Objectives: The primary objective of this trial is to determine whether different types of anaesthesia [regional versus general] given to infants undergoing inguinal hernia repair result in equivalent neurodevelopmental outcomes. Secondary objectives are to describe the frequency and characteristics of apnoea in the post-operative period after both regional and general anaesthesia for inguinal hernia repair in infants, and determine the factors associated with apnoea.

Study population: 660 infants of postmenstrual age 60 weeks age or less, scheduled for inguinal hernia repair under anaesthesia. Exclusion criteria include recognised risk factors for adverse neurodevelopmental outcome or previous exposure to general anaesthesia. Infants born at less than 26 weeks gestation will be excluded.

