1.4.1 Anaesthesia in infancy

Anaesthesia in infants and neonates is becoming increasingly common. In 2002 in Western Australia 7.8% of male and 3.2% of female children aged less than 1 year had anaesthesia [2]. Of these infants 10% of the males and 20% of the females had the anaesthesia during their first 28 days of life. The use of anaesthesia in infants (and indeed in the foetus) is likely to further increase as more surgical options are available, as there is a greater appreciation of the ethical and developmental need for anaesthesia to reduce nociceptive stimuli, and as advances in anaesthesia practice reduce the short-term morbidity and mortality.

General anaesthesia in infants and neonates usually involves a volatile anaesthetic (e.g. sevoflurane, isoflurane or halothane) or an intravenous anaesthetic (e.g. barbiturate or propofol). These act via the GABA receptor. Anaesthesia may also be provided with awake regional nerve blockade using a local anaesthetic agent (for example spinal anaesthesia).

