1.4.2 Apoptosis and neurodevelopment

Several studies have consistently demonstrated that neonatal rats, mice and guinea pigs exposed to GABA agonists, such as volatile anaesthetics, or to NMDA antagonists such as ketamine, have widespread neuronal apoptotic lesions and delays in achieving some developmental goals [3-7]. In rats the injury is most obvious when they are exposed to anaesthesia during the period of synaptogenesis at the age of 7 days. Recently neurotoxicity has also been demonstrated in prenatal rhesus monkeys exposed to ketamine [8].

The ontogeny of NMDA and GABA receptors is consistent with the existence of a period of potential neuro-toxicity mediated by anaesthetics. The composition of neonatal NMDA receptor subunits differs compared with adults [9], and the GABA receptor is excitatory rather than inhibitory in the neonatal brain [10].

Correlation of the stages of animal neural development with that of human brain development is imprecise. In the rat the period of synaptogenesis lasts from day 4 to day 10 and peaks at day 7. In the human this equates to the period from approximately the third trimester to one year of age. Thus, in theory humans may be susceptible to anaesthesia toxicity anywhere from ante-partum to late infancy.

Interspecies variation limits the generalisation of the animal data to humans. Similarly experimental conditions for rodents may be significantly different to conditions experienced by neonates undergoing surgery and anaesthesia. Differences include, concurrent oxygen, nutrition or blood glucose management, the dose of the agents used, the different organisation and plasticity of the human brain [1, 11, 12]. Compared with the time of exposure to anaesthesia, the developmental period is considerably longer in a human compared to a rat, however from a molecular biological perspective, apoptosis could be triggered irrespective of the usual period of neurodevelopment. Due to greater plasticity it is possible that the human brain is capable of accommodating greater apoptotic injury than the rat brain without any clinically significant effect to neurological development, although the evidence for this premise is limited.

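### The synopsis excludes any previous general anaesthesia, but section 4.3 excludes only some agents over an unclear period, so previously anaesthetised infants can be randomised, and nothing requires this to be recorded

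*Protocol*

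**What the plan says.** The synopsis, under study population, states: "Exclusion criteria include recognised risk factors for adverse neurodevelopmental outcome or previous exposure to general anaesthesia". It names no agent and no period.

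Section 4.3, the list against which sites screen under section 4.4, has instead: "Previous exposure to volatile anaesthesia or benzodiazepines as a neonate or in the third trimester in utero". The same list sets the upper age limit: "Any child older than 60 weeks postmenstrual age".

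The rationale is wider than section 4.3. Section 1.4.2 reports that young animals exposed to GABA agonists "or to NMDA antagonists such as ketamine, have widespread neuronal apoptotic lesions". On the susceptible period it says: "In the human this equates to the period from approximately the third trimester to one year of age". Section 1.4.1 lists barbiturates and propofol beside the volatile agents as general anaesthetics used in infants and acting via the GABA receptor. Section 1.4.2 names ketamine as an NMDA antagonist, and section 5.6 bars it during the study anaesthetic.

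Earlier anaesthetic exposure is not among the history items in section 3.5.4. Section 3.5.1 ties eligibility data to the inclusion and exclusion criteria. Section 8.1 analyses the primary outcome per protocol.

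**The concern.** The trial asks whether a general anaesthetic in infancy affects IQ at 5 years, using the awake regional arm as the comparator without general anaesthetic exposure. An infant who has already had a general anaesthetic does not fit that description. The synopsis says such infants are excluded; the operative text does not. Sites working from section 4.3 can enrol infants whom a reader of the synopsis would believe absent.

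In an equivalence trial, anything that narrows the true contrast between arms makes the equivalence claim easier to reach. Nothing later in the protocol reliably corrects for these infants. They satisfy section 4.3, so they are not protocol violations, and the per-protocol analysis does not by itself remove them. With no baseline item, they could not be identified dependably for a sensitivity analysis.

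**Working it through.** **Comparing the two rules.** Section 4.3 can be read in two ways.

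| Earlier exposure | Synopsis | 4.3, time limit on both agents (plain reading) | 4.3, time limit on benzodiazepines only |
|---|---|---|---|
| Volatile agent, neonatal period | excluded | excluded | excluded |
| Volatile agent, after neonatal period | excluded | eligible | excluded |
| General anaesthesia with ketamine, propofol or a barbiturate | excluded | eligible | eligible |
| Benzodiazepine, neonatal or third trimester | not mentioned | excluded | excluded |

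The intravenous agents are admitted on both readings. The later volatile exposure depends on how the sentence is parsed. The period after the neonatal stage is not empty. If a neonate is taken as an infant in the first 28 days (an assumption; the term is not defined), one born at 40 weeks leaves that stage at 44 weeks postmenstrual age and is eligible to 60, which leaves up to 16 weeks.

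**The plan's own figure.** Section 8.3 gives: margin 5, SD 15, one-sided alpha 0.025, power 90% at a true difference of 1 point, 598 evaluable infants. Equal allocation is assumed, so 299 per arm.

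- Simple formula: n = 2 × 15² × (1.960 + 1.282)² / (5 − 1)² = 296 per arm, 592 in total.
- Two one-sided tests, both tails: SE = 15 × √(2/299) = 1.227. The interval lies within ±5 if the estimate is within ±(5 − 1.960 × 1.227) = ±2.595. At a true difference of 1, power = Φ((2.595 − 1)/1.227) − Φ((−2.595 − 1)/1.227) = 0.902.
- The smallest n reaching 90% is 298 per arm with the normal critical value and 299 with the t value. The 598 is reproduced.

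**Effect of earlier exposure.** Let d be the true effect of one exposure and f the proportion previously exposed, the same in both arms by randomisation.

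- Threshold model (a first exposure gives the full effect, a second adds nothing): every infant in the general arm and a fraction f of the regional arm carry the effect, so the contrast is d(1 − f).
- Additive model: earlier exposure shifts both arms equally, so the contrast stays d.
- Repeat exposure worse than additive: the contrast exceeds d.

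Under the threshold model, with 299 per arm, the chance of declaring equivalence is Φ((2.595 − d(1 − f))/1.227); the other tail is negligible.

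| f (assumed) | Contrast, d = 5 | Chance, d = 5 | Contrast, d = 6 | Chance, d = 6 |
|---|---|---|---|---|
| 0% | 5.00 | 2.5% | 6.00 | 0.3% |
| 2% | 4.90 | 3.0% | 5.88 | 0.4% |
| 5% | 4.75 | 4.0% | 5.70 | 0.6% |
| 10% | 4.50 | 6.0% | 5.40 | 1.1% |
| 20% | 4.00 | 12.6% | 4.80 | 3.6% |

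To bring a true 6-point difference down to the margin, f must reach 1 − 5/6 = 16.7%. Under the additive model every row equals the first.

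**The case against.** A synopsis is a summary, and it could be said that the detailed list simply governs. That settles which rule sites apply, not which was intended. The narrower rule also sits badly with the protocol's own rationale.

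Four stronger readings are tempting, and the protocol does not support them.

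- **Any difference is diluted.** Previously exposed infants are randomised to both arms. Dilution requires a threshold-type effect, and the protocol does not say which form to expect.
- **The distortion is large.** No frequency of earlier exposure is given. The only nearby figures, in section 1.4.1, are 7.8% of boys and 3.2% of girls anaesthetised before one year in a general population, which may include hernia repairs themselves. Other exclusions in section 4.3, such as heart disease needing surgery or known neurological injury, may already remove some exposed infants. At low f the change is modest, and it is largest in absolute terms at the margin itself.
- **Most of an infant's life before surgery is uncovered.** Any such percentage depends on the undefined word neonate and on extreme ages at birth and entry. Days not covered are also not infants exposed.
- **The 5-year visit misses later exposure.** The 2-year visit asks for "Exposure to any anaesthetic agents or benzodiazepines since discharge from hospital after hernia repair", which takes in the rest of the protocol's susceptible period after discharge. The 5-year visit collects "Details of all hospital attendances and admissions to hospital since 2 year assessment", so hospital anaesthetics between 2 and 5 years are partly captured, and those ages lie outside that period. This is not a main defect.

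What remains is the conflict between the synopsis and section 4.3, the ambiguous sentence, and the missing baseline item.

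**Conclusion.** The point holds as an internal inconsistency in eligibility with a possible, not a demonstrated, bias. The synopsis and section 4.3 exclude different infants. On either reading, section 4.3 admits infants previously given intravenous anaesthetics that the protocol itself treats as relevant; on the plain reading it also admits later volatile exposure. Neither the baseline history nor the per-protocol analysis deals with them.

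The size cannot be derived from the protocol. With 299 per arm, SD 15, a threshold effect and a true difference of 5 points, false equivalence goes from 2.5% to about 4% at an assumed 5% exposed and 6% at an assumed 10%. With an additive effect it stays at 2.5%. The change is worth making because it is cheap and protects the contrast on which the trial rests.

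**What to change.** 1. Replace the last item of section 4.3 with one criterion, consistent with the synopsis, that excludes previous exposure to a general anaesthetic, volatile or intravenous and including ketamine, up to randomisation. State the agents and the period explicitly. Say separately how in utero exposure and benzodiazepines are handled, and define neonate if the word is kept. Align the synopsis with the result.
2. Add earlier anaesthetic exposure (agent, date, occasion) to the baseline history in section 3.5.4, so that the primary analysis can be repeated without exposed infants. If infants have already been enrolled under the present wording, collect the item for them from their records.

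The cost is a reworded criterion and one baseline item. Some otherwise eligible infants will be excluded; the protocol does not allow their number to be estimated. The 598 evaluable and 660 enrolled stand, since earlier exposure does not enter that calculation.
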